pSS Table 8 lists the complete sampling schedule for assessment of the PK of branebrutinib, metabolites, and concomitant medications in subjects with pSS.

To assess steady-state concentrations of branebrutinib, a total of 5 predose PK samples (approximately 4 mL each) will be drawn from all study subjects at Week 0 (Day 1), Week 4 (Day 29), Week 8 (Day 57), Week 16 (Day 113), and Week 24 (Day 169). (Note that these samples will be drawn within a 1-hour window before the next dose is administered.) For subjects at preselected sites with extended sampling, predose PK samples collected at Week 8 (Day 57) will also be aliquoted to assess metabolite concentrations.

For postdose sampling, all study subjects will have branebrutinib PK samples drawn at Week 0 (Day 1), Week 8 (Day 57), and Week 24 (Day 169) at the 0.5, 1, 2, and 4-hour time points, a total of 14 samples. (Note that these samples will be drawn within ± 15 min from the given time points.) For subjects at preselected sites with extended sampling, postdose PK samples will be aliquoted to assess metabolite concentrations at these time points.

Protocol Amendment No.: 04

In addition, for subjects at preselected sites with extended sampling, a total of 7 postdose PK samples will be drawn and assessed for both branebrutinib and metabolite concentrations at Week 0 (Day 1) and Week 8 (Day 57) at approximately 06:00 hours, and from 08:00 to 10:00 hours (flexible window), and from 10:00 to 12:00 hours (flexible window). Samples will also be collected at Week 0 (Day 2) at approximately 24:00 hours postdose (predose of branebrutinib on Day 2). Efforts should be made to collect the samples within these windows; however, any sample drawn outside the prespecified window will not be considered a protocol deviation. Both planned and actual time points at which the blood samples will be taken will be recorded and used in analysis and modeling.

Concomitant Medications

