d Blood samples for the PK assessment of branebrutinib concentrations will be taken predose in all study subjects on Week 0 (Day 1), and Week 8 (Day 57) and postdose at Week 8 (Day 57) at approximately 0.5, 1, 2, and 4 hours after dosing. At Week 4 (Day 29), samples will be taken predose only for the assessment of steady-state trough concentration of branebrutinib.

At preselected clinical sites with extended sampling: blood samples will be taken from subjects at Week 0 (Day 1) and Week 8 (Day 57) at 0 hours (predose), and postdose at approximately 0.5, 1, 2, 4, and at 6 hours and from 8-10 hours (flexible window), 10-12 hours (flexible window), and at Week 0 (Day 2) at 24 hours after dosing (predose of branebrutinib on Day 2); collected blood samples will be divided into 2 tubes at each time point for the PK assessment of branebrutinib and its metabolites concentrations.

- Blood samples for PK assessment of relevant concomitant medications that are sensitive substrates of CYP2C8 and other potentially relevant drug metabolizing enzymes and P-gp transporter may be measured (post-hoc); as such, the levels of exposure for subjects receiving PBO and active treatment will be collected at Week 0 (Day 1) and Week 4 (Day 29) predose and 2 hours postdose.
- ^g Blood sample for PK of abatacept not required if this is subject's EOT visit.

k First dose of abatacept is to be administered at the Week 12 visit.

When multiple assessments are conducted at a single visit, the following is the order in which they should be performed:

- 1. Patient-reported Outcomes (eg, SGA, EQ-5 D-5 L, etc)
- 2. Safety assessments (eg, vitals, AEs)
- 3. Investigator-administered Assessments (eg, PGA, joint count, etc)
- 4. Laboratory tests (eg, safety laboratory tests, PK assessments, biomarker assessments)
- 5. Treatment dosing

Protocol Amendment No.: 04

Date: 01-Dec-2021

Approved v2.0 930168072 2.0

RA Table 3 Procedural Outline Branebrutinib Study IM014029: Open-label Abatacept Therapy (Week 14 to Week 28)

Procedure	Week 14 D99 (± 3 d) V7	Week 16 D113 (± 3 d) V8	Week 20 D141 (± 3 d) V9	Week 24 D169 (± 3 d) V10 (EOT) ^a	Week 28 D197 (±3 d) V11 Safety FU	Notes
Patient-reported Outcomes						
SGA of Disease Activity	X	X	X	X	X	Collected on eCOA device (refer to Section RA 8.1.1.4).
HAQ-DI	X	X	X	X	X	Collected on eCOA device (includes pain VAS for ACR calculation; refer to Section RA 8.1.1.1).
EQ-5 D-5 L				X	X	Collected on eCOA device (refer to Section RA 8.1.1.3).

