Branebrutinib PK samples will be analyzed by a vendor using a validated assay. Plasma samples for metabolites will be analyzed by the BMS bioanalytical laboratory. These analyses will be reported separately. The BMS laboratory will be unblinded before the end of the study and will not communicate unblinded information to the BMS study teams where the data allow. Individual subject PK parameter values for branebrutinib will be derived from plasma concentration data versus time by noncompartmental methods with a validated PK analysis program. Actual times will be used for the analyses.

For all study subjects, the branebrutinib PK parameters listed below will be calculated and summarized with data up to 4 hours postdose. Accumulation ratios for Cmax and AUC(0-4) will also be calculated.

Cmax	Maximum observed concentration
Tmax	Time to maximum concentration
Ctrough	Trough observed plasma concentration
AUC(0-4)	Area under the plasma concentration-time curve from time zero to the 4-hour dosing period

For subjects at preselected sites with extended sampling, separate PK concentrations of branebrutinib and select metabolites at all timepoints will be summarized by timepoint. The branebrutinib parameters listed below will be calculated and summarized.

Cmax	Maximum observed concentration
Tmax	Time to maximum concentration
AUC(0-T)	Area under the plasma concentration-time curve from time zero to time of last quantified concentration
AUC(TAU)	Area under the concentration-time curve to the end of the dosing period
Ctrough	Trough observed plasma concentration

RA Table 9 lists the complete sampling schedule for assessment of the PK of branebrutinib, metabolites, and concomitant medications in subjects with RA.

To assess steady-state concentrations of branebrutinib, a total of 2 predose PK samples (approximately 4 mL each) will be drawn from all study subjects at Week 0 (Day 1) and Week 4 (Day 29) (Note that these samples will be drawn within a 1-hour window before the next dose is administered.) For subjects at preselected sites with extended sampling, predose PK samples collected at Week 8 (Day 57) will be aliquoted to assess metabolite concentrations.

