For postdose sampling, all study subjects will have branebrutinib PK samples drawn at Week 0 (Day 1) and Week 8 (Day 57) at the 0.5, 1, 2, and 4-hour time points. (Note that these samples will be drawn within ± 15 min from the given time points.) For subjects at preselected sites with extended sampling, postdose PK samples will be aliquoted to assess metabolite concentrations at these time points.

In addition, for subjects at preselected sites with extended sampling, postdose PK samples will be drawn and assessed for both branebrutinib and metabolite concentrations at Week 0 (Day 1) and Week 8 (Day 57) at approximately 06:00 hours, and from 08:00 to 10:00 hours (flexible window) and from 10:00 to 12:00 hours (flexible window). Samples will also be collected at Week 0 (Day 2) approximately 24:00 hours postdose (predose of branebrutinib on Day 2). Efforts should be made to collect the samples within these windows; however, any sample drawn outside the prespecified windows will not be considered a protocol deviation. Both planned and actual time points at which the blood samples will be taken will be recorded and used in analysis and modeling.

Concomitant Medications

Concomitant medications that are sensitive substrates of CYP2C8 and other potentially relevant drug metabolizing enzymes that may lead to drug-drug interaction with branebrutinib and P-gp transporter may be measured (post-hoc) for the levels of exposure for subjects receiving PBO and active treatment. Samples for the PK assessment of the relevant concomitant medications will be collected at Week 0 and Week 4 from all study subjects. Samples for PK analysis collected from subjects receiving branebrutinib or PBO will be analyzed for HCQ and other relevant concomitant comedications provided that these subjects are receiving HCQ and other relevant concomitant comedications.

Detailed instructions for the collection, labeling, processing, storage, shipping, and disposition of all PK blood samples are provided in the Laboratory Manual.

RA Table 9 PK Sampling Schedule for Branebrutinib, Metabolites, and Concomitant Medications

	Study Week		Time (Relative to Branebrutinib Dose) Hours:Minutes	Branebrutinib	from	Comments
1	0	Predose	00:00	X		 Predose PK samples will be collected from all study subjects to assess concentrations of

Protocol Amendment No.: 04

RA Table 9 PK Sampling Schedule for Branebrutinib, Metabolites, and Concomitant Medications

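### RA Table 2 footnote d omits the Day 1 postdose PK samples that RA 8.5 and RA Table 9 require; if followed, it leaves accumulation ratios uncomputable outside the extended-sampling sites

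*Combined protocol and SAP*

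**What the plan says.** RA Table 2 (RA 1.3) has a row for standard branebrutinib PK samples, marked at Weeks 0, 4 and 8. Its notes column points to RA 8.5 and RA Table 9. Footnote d to that row gives the times. It applies to the whole study population and sets predose draws for the first and third of those visits. Its postdose draws are limited to one visit: "postdose at Week 8 (Day 57) at approximately 0.5, 1, 2, and 4 hours after dosing". The middle visit has a trough sample and nothing else: "At Week 4 (Day 29), samples will be taken predose only". No Day 1 postdose draw is listed.

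The footnote that follows concerns a separate group: "At preselected clinical sites with extended sampling: blood samples will be taken from subjects at Week 0 (Day 1) and Week 8 (Day 57". That group has predose and postdose times on both days, including 0.5, 1, 2 and 4 h.

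RA 8.5 differs from footnote d. It sets the same four postdose times at two visits, not one: "all study subjects will have branebrutinib PK samples drawn at Week 0 (Day 1) and Week 8 (Day 57". RA Table 9, which RA 8.5 presents as the full schedule, marks those four Day 1 times for all subjects. RA 8.5 also plans Cmax, Tmax, Ctrough and AUC(0-4) for all study subjects from data through 4 h, and says: "Accumulation ratios for Cmax and AUC(0-4) will also be calculated".

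Two stated counts are also relevant. RA 8.5 gives "a total of 2 predose PK samples", naming Day 1 and Week 4. The standard postdose sentence of pSS 8.5 gives "a total of 14 samples".

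**The concern.** Footnote d cannot be followed together with RA 8.5 and RA Table 9. It is not silent on postdose sampling: it gives a specific schedule that looks complete. The next footnote lists Day 1 postdose times only for preselected sites, so the omission for everyone else can look deliberate. RA 8 makes adherence to the schedule of activities mandatory.

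An accumulation ratio divides a later value by the first-dose value. Without Day 1 postdose samples there is no Day 1 Cmax or AUC(0-4), and a first-dose profile cannot be collected afterwards. PK parameters of branebrutinib are a listed endpoint (RA 9.3.4).

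**Working it through.** **Step 1: count branebrutinib samples per RA subject outside the extended-sampling group.**

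| Source | Predose | Postdose | Total |
|---|---|---|---|
| RA Table 2 footnote d | Day 1, Week 4, Week 8 = 3 | Week 8: 1 x 4 = 4 | 7 |
| RA 8.5 text | Day 1, Week 4 = 2 | Day 1 and Week 8: 2 x 4 = 8 | 10 |
| RA Table 9 | Day 1, Week 4, Week 8 = 3 | Day 1 and Week 8: 2 x 4 = 8 | 11 |

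RA 8.5 prints no overall total; the 10 adds its predose and postdose sentences. Footnote d falls short of RA Table 9 by 11 - 7 = 4 samples: Day 1 at 0.5, 1, 2 and 4 h.

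**Step 2: can the ratios be formed?** Taking Week 8 as the later profile, each ratio is the Week 8 value divided by the Day 1 value, for Cmax and for AUC(0-4).
- RA Table 9: Day 1 and Week 8 profiles both exist, so both ratios can be computed.
- Footnote d: the only Day 1 sample precedes the first dose, so neither ratio has a denominator.

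**Step 3: how many subjects?** RA 9.1 plans 60 branebrutinib and 20 placebo subjects. RA 8.5 says placebo samples are not assayed for branebrutinib, so the base is 60. Let f be the share of branebrutinib subjects in the extended-sampling group, who keep their Day 1 postdose samples under their own footnote. The documents shown do not give f, so the range is shown.

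| f | Without ratios if footnote d is followed: 60 x (1 - f) |
|---|---|
| 0% | 60 |
| 10% | 54 |
| 25% | 45 |
| 50% | 30 |
| 75% | 15 |
| 100% | 0 |

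**Step 4: the stated counts.**
- RA 8.5 predose: 2 stated. This matches the two visits in its own sentence, but RA Table 9 and footnote d both give 3, adding Week 8.
- pSS 8.5 standard postdose: 14 stated. The visits and times listed (Weeks 0, 8 and 24; four times each) give 3 x 4 = 12, as does pSS Table 8. Two visits x 7 postdose points (4 standard + 3 extended) would give 14, but that is not the schedule the sentence describes.
- pSS 8.5 predose: 5 stated. Weeks 0, 4, 8, 16 and 24 give 5, so it reproduces.
- pSS 8.5 extended postdose: 7 stated. Three on Day 1 + 3 at Week 8 + 1 on Day 2 = 7, so it reproduces.

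**The case against.** The strongest reply is that the documents largely indicate which source to use. The row carrying footnote d refers to RA 8.5 and RA Table 9, and RA 8.5 treats RA Table 9 as the full schedule. Samples are lost only where a site reads the footnote and does not follow the reference. Collection instructions also sit in a Laboratory Manual that is not available here. This stands as mitigation and makes the loss conditional. It does not remove the conflict, because a site that follows the reference finds two different schedules and no statement of which governs.

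The second reply is that little is at stake. PK is an exploratory objective in RA Table 4. RA 8.5 also assesses accumulation from predose concentrations, which footnote d keeps. RA 4.5 reports negligible accumulation in healthy subjects. Extended-sampling RA subjects and all pSS subjects would still have Day 1 and Week 8 profiles. This rightly limits the weight of the point. Predose values cannot, however, replace Cmax or AUC(0-4). RA 4.5 gives a mean half-life under 2 hours in healthy subjects; if that holds in RA, 24 hours is more than 12 half-lives and less than 0.03% of the drug remains. The plan also promises these ratios for all RA study subjects.

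Third, the RA 8.5 predose count is tied to steady-state assessment, and the same paragraph mentions Week 8 predose samples at preselected sites. The text therefore knows of that draw, and the discrepancy is an incomplete count rather than a separate design. The pSS total misdirects no draw, because its visits and times are listed correctly.

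**Conclusion.** The contradiction is real. Footnote d omits Day 1 postdose samples that RA 8.5 and RA Table 9 require of all subjects. Followed as written, it leaves every branebrutinib subject outside the extended-sampling group, 60 x (1 - f), without a Day 1 Cmax or AUC(0-4), and so without either planned ratio. This assumes the planned 60 branebrutinib subjects and a site that does not act on the cross-reference. The effect is limited to PK; the primary ACR50 analysis does not use these samples.

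A reader might infer three stronger conclusions, none of which the documents support:
- **Most subjects would lose the ratios.** That needs f below 50%, and f is not given.
- **The samples will be lost.** The row's reference to RA 8.5 and RA Table 9 makes this a risk only.
- **The stated sample totals are generally unreliable.** Of the four checked, two fail (RA predose 2 against 3; pSS postdose 14 against 12) and two reproduce (pSS 5 and 7). The two failures are secondary text errors.

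**What to change.** Reconcile RA Table 2 footnote d, the RA 8.5 text and RA Table 9 into one list of visits and times, and state which location governs. If accumulation ratios are kept for all study subjects, that list must include the Day 1 postdose times. If they are not kept for all, RA 8.5 should say for whom they will be calculated.

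In the same revision, reconcile the RA 8.5 predose count of 2 with the 3 visits in RA Table 9 and footnote d, and the pSS 8.5 postdose total of 14 with the 12 its own visits and times give.

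The cost is text correction in an amendment or administrative letter. No samples beyond those already in RA Table 9 are needed.

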Patient-reported Outcomes						
SGA of Disease Activity	X	X	X	X	X	Collected on eCOA device (refer to Section RA 8.1.1.4).
HAQ-DI	X	X	X	X	X	Collected on eCOA device (includes pain VAS for ACR calculation; refer to Section RA 8.1.1.1).
EQ-5 D-5 L	X				X	Collected on eCOA device (refer to Section RA 8.1.1.3).
PROMIS-Fatigue 6 a	X				X	Collected on eCOA device (refer to Section RA 8.1.1.2).
Safety Assessments						
Complete Physical Examination	X				X	
Targeted Physical Examination		X	X	X		
Body Weight	X				X	
Vital Signs	X	X	X	X	X	Temperature (ear or oral), respiratory rate, seated BP, and seated heart rate; BP and heart rate should be measured after the subject has been resting quietly for at least 5 minutes.
ECG	X	X	X	X	X	ECGs should be recorded after the subject has been supine for at least 5 minutes.
Concomitant Medication Use	X	X	X	X	X	
AE and SAE Assessment	X	X	X	X	X	Nonserious AEs must be collected from the time of the first dose of the study drug through the date of the follow-up or last visit.
Clinical Assessments						
Tender/Swollen/Painful Joint Count (68/66)	X	X	X	X	X	Performed by independent joint count assessor. Collected on eCOA device (Refer to Section RA 8.1.2.1).

RA Table 2 Procedural Outline Branebrutinib Study IM014029 (Week 0 to Week 12)

Procedure	W0 D1 V2	W2 D15 (± 3 d) V3	W4 D29 (± 3 d) V4	W8 D57 (± 3 d) V5	W12 D85 (± 3 d) V6 (EOT) ^a	Notes
PGA	X	X	X	X	X	Performed by investigator. Collected on eCOA device (Refer to Section RA 8.1.2.2).
MRI of the hand/wrist that is clinically most swollen at screening will be imaged using a whole-body MRI system (RAMRIS) b					X	Perform within 7 days of scheduled visit (Refer to Section RA 8.1.2.3).
Composite Assessments of Disease Activity						
CDAI	X	X	X	X	X	Composite score calculated programmatically (Refer to Section RA 8.1.3).
SDAI	X	X	X	X	X	Composite score calculated programmatically (Refer to Section RA 8.1.3).
DAS28-CRP, DAS28-ESR	X	X	X	X	X	Composite score calculated programmatically (Refer to Section RA 8.1.3).
ACR 20/50/70	X	X	X	X	X	Composite score calculated programmatically (Refer to Section RA 8.1.3).
Laboratory Tests						
Hematology	X	X	X	X	X	
Serum Chemistry Panel	X	X	X	X	X	
Lipid Panel (Fasting)	X		X	X	X	
Urinalysis	X	X	X	X	X	
eGFR	X	X	X	X	X	
Beta-2-microglobulin	X	X	X	X	X	
ESR ^c	X	X	X	X	X	Performed at site.

RA Table 2 Procedural Outline Branebrutinib Study IM014029 (Week 0 to Week 12)

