The effects of BTK inhibition by branebrutinib have been documented in pharmacology studies, and the potential for benefit has been demonstrated by nonclinical studies using mouse models of RA (see details of nonclinical toxicology findings and potential clinical benefits of branebrutinib in Section 1.5.1 Master Protocol: Benefit/Risk Assessment).

With the exception of an unrelated SAE that was consistent with the subject's medical history, AEs in the FIH study (Study IM014001³⁷) were mild to moderate, reversible, and consistent with expectations based on nonclinical experience.

Based upon nonclinical toxicology findings and the mechanism of action of the compound (immunosuppression), BMS has also proactively implemented additional assessments, frequent study visits for safety assessments, risk mitigation approaches, and blinded safety reviews by BMS and an independent external DMC (see details in Section 1.5.1 Master Protocol: Benefit/Risk Assessment).

All subjects in the RA sub-protocol will receive either branebrutinib or PBO treatment for a maximum of 12 weeks while receiving protocol-defined SOC therapy for their RA. All subjects in the RA sub-protocol will also receive open-label abatacept from Week 12 to Week 24.

The risk for DDIs of branebrutinib with substrates of a number of enzymes and transporters are expected to be minimal, with the exception of drugs that are sensitive substrates of CYP2C8 and P-gp as a weak inhibitor (which may be restricted or excluded based on their therapeutic window and metabolism), as are developmental and reproductive effects of the study treatment in WOCBP (see details in Section 1.5 Master Protocol: Benefit/Risk Assessment).

RA 2.2.2 Open-label Therapy with Abatacept

Abatacept, a soluble fusion protein that consists of the extracellular domain of human CTLA-4 linked to the modified Fc (hinge, CH2, and CH3 domains) portion of human IgG1, is a selective co-stimulation modulator that inhibits T cell activation by binding to CD80 and CD86 molecules on antigen-presenting cells, thereby inhibiting interaction with CD28.

Abatacept is a biologic compound approved for the treatment of patients with active RA (see the abatacept IB⁴⁸ for properties and mechanisms of action of abatacept).

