- ACR20, ACR50, and ACR70 response at Week 24 compared to baseline
- Change from baseline at Week 24 in PROMIS Fatigue 6 a

Safety

To evaluate the safety and tolerability of switching from branebrutinib or PBO to abatacept in subjects with RA

Number and proportion of subjects experiencing SAEs, AEs, and abnormalities in laboratory parameters, vital signs, and ECGs

Exploratory

[figure not shown]
• Evaluate the PK of branebrutinib and metabolites of clinical interest

Protocol Amendment No.: 04 Date: 01-Dec-2021

225

; RNA = ribonucleic acid;

Simplified Disease Activity Index;

RA 4 STUDY DESIGN

;

RA = rheumatoid arthritis;

RA 4.1 Overall Design

This is a double-blind, PBO-controlled multicenter study to assess the effect of branebrutinib treatment and branebrutinib followed by abatacept (also named BMS-188667 and OrenciaTM) 125 mg SC QW in subjects with moderate to severe adult-onset RA.

SAE = serious adverse event;

SDAI =

- The RA study population will consist of male and female subjects aged 18 years (or age of majority) to 75 years inclusive at screening with moderate to severe adult-onset RA.
- Approximately 80 subjects will be randomized to the RA sub-protocol. Sample size considerations are presented in Section RA 9.1 Sample Size Determination.
- For all subjects there will be a 12-week double-blind PBO-controlled treatment period in which subjects will receive branebrutinib 9 mg or branebrutinib PBO. Note: the last day of dosing of branebrutinib or PBO in the RA sub-protocol should be the day prior to the Week 12/Day 85 visit.
- Blinded treatment assignment will be conducted by randomization on Day 1 and managed by IRT. Subjects will undergo screening evaluations to determine eligibility within 28 days prior to administration of study medication. After successfully meeting entry criteria and completing

screening assessments, subjects will be randomized (3:1 ratio) in a blinded manner to branebrutinib 9 mg or PBO QD.

- No stratification will be imposed at randomization in this sub-protocol.
- The total duration of participation in the RA sub-protocol will be approximately 32 weeks and will be divided into the following periods: screening (up to 4 weeks), double-blind PBO-controlled treatment with branebrutinib for 12 weeks (Week 0 to Week 12), open-label abatacept treatment for an additional 12 weeks (Week 12 to Week 24), and follow-up (4 weeks).

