The investigator will perform all efficacy- and safety-related assessments, except for the 66/68 joint count, which will be performed by an independent joint count assessor who is blinded to all other assessments (eg, safety evaluation, laboratory test assessments, etc). For both the investigator and independent joint count assessor, every effort must be made to ensure that the same individual performs the specified required assessments al all visits across the study for each subject. Visit scheduling must take into account the availability of necessary assessors. Training and instruction will be provided to ensure that joint count assessments are conducted in a standard manner across sites. If the evaluator(s) is unable to complete the evaluation, then a qualified individual with overlapping experience may perform the evaluation. Documentation of the individual performing the evaluation is to be recorded in source documents.

The PI, or sub-investigator designated by the PI and confirmed by the Sponsor, may be a Doctor of Medicine or Doctor of Osteopathy, Physician's Assistant, or Nurse Practitioner with experience in the diagnosis and management of subjects with RA.

All assessments should be performed or administered prior to study drug administration unless otherwise indicated. Assessments are to be conducted at approximately the same time of day throughout the duration of the study for a given subject. Assessments conducted on Day 1, Week 0 must be performed per protocol (assessments performed as part of SOC may not be used in lieu of these assessments). Procedures not specified in the protocol that are part of standard care may be performed if they do not interfere with study procedures; any data arising from such procedures are not to be reported in the eCRF.

RA 8.1.1 Patient-reported Outcomes

Patient-reported health outcomes, as studied in RA, include questionnaires and scales that focus on general health, rheumatology, and RA disease-specific issues. The results of these health outcomes will be recorded electronically on eCOA devices provided by the Sponsor or designee to the sites.

RA 8.1.1.1 Health Assessment Questionnaire Disability Index (HAQ-DI)

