Sixty-six joints (68-joint count minus both hips) will be classified as either swollen or not swollen. Swelling is defined as palpable fluctuating synovitis of the joint. Swelling secondary to osteoarthrosis will be assessed as not swollen, unless there is unmistakable fluctuation.

Joint assessments of 1 particular subject should be performed (if at all possible) by the same assessor throughout the study to minimize inter-observer variation.

Missing, replaced, ankylosed, or arthrodesed joints will be identified by the assessor at the screening visit and will be excluded from evaluation during the study. The locations (or a listing) of surgical procedures should be documented in the subject's source documents/eCRF pages.

RA 8.1.2.2 Physician Global Assessment of Disease Activity (PGA)

The PGA is a VAS that the physician uses to assess the manner in which RA has affected the RA subject (APPENDIX 26).

RA 8.1.2.3 RA Magnetic Resonance Imaging (MRI) Scoring System

The MRI scanners used in the RA sub-protocol study must be deemed qualified by the Sponsor-assigned core imaging lab prior to subject scans. The hand/wrist that is clinically most swollen at screening will be imaged using a whole-body MRI system. The screening visit MRI is considered the baseline MRI assessment for this study. If a subject requires rescreening, the MRI results obtained at the initial screening visit may be used for the rescreening, if the MRI was obtained within 30 days of randomization. It is recommended that sites should schedule 2 MRI appointments with the radiology department 7 days apart in the event that an MRI exam needs to be repeated due to technical difficulties. MRI exams with quality issues identified at the investigator site or core imaging lab should be repeated within 7 days of notification.

The same hand/wrist that was imaged at screening will be imaged at Week 12 and Week 24 on the same MRI scanner as the one used at screening. The screening visit MRI is to be performed approximately 14 days prior to randomization. Week 12 and Week 24 MRI exams are to be performed within 7 days of both scheduled Week 12 visit and Week 24 visits. Subjects who terminate the study early require an MRI at the EOT visit only if that visit is ≥ 4 weeks from the date of randomization or ≥ 4 weeks from Week 12 and should have the EOT MRI no more than 7 days from the EOT visit.

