^a Concentrations of concomitant medications that are sensitive substrates of CYP2C8 and other potentially relevant drug metabolizing enzymes that may have a drug-drug interaction with branebrutinib and P-gp transporter may be evaluated post-hoc for subjects receiving PBO and active treatment at predose of branebrutinib on Day 1 and Day 29.

b Subjects being treated with prescription concomitant medications will be informed to bring them to the clinic on Day 1 and Day 29 for simultaneous dosing with branebrutinib, but only when it is safe for subjects and operationally feasible. This should be based on the investigator's discretion with consideration that the medications which should not be delayed until the time of dosing in the clinic should be taken at home. The self-reported time for all prescription medications taken at home should be recorded as accurately as possible.

^c PK sample must be drawn before the branebrutinib dose is administered on Day 2.

RA 8.5.1 PK and Immunogenicity of Abatacept (Weeks 12 and Later)

The PK samples for abatacept and for immunogenicity analysis will be taken at predose at clinic visits for all subjects. The sampling schedule for abatacept is provided in RA Table 10.

Samples from all subjects receiving abatacept treatment will be analyzed for abatacept concentration as well as for antidrug antibodies (ADAs) and abatacept-neutralizing potential. Trough samples within a 30-minute window before each dose will be collected, as well as samples at the FU visit at early discontinuation or the EOT.

RA Table 10 PK and Immunogenicity Sampling Schedule for Abatacept

Study Day of Sample Collection	Study Week of Sample Collectio n	Event	Time (Relative to Branebrutinib Dose and Abatacept Dose) Hour:Minute	Blood Sample for PK and Immunogenicity/ Abatacept	Comment – All Samples Mandatory for All Subjects
85	12	Predose	00:00	X	Before the first dose of abatacept
99	14	Predose	00:00	X	Before the third dose of abatacept
113	16	Predose	00:00	X	
141	20	Predose	00:00	X	
169	24		00:00	X	Since abatacept is not administered at this visit, this blood sample is not collected predose; this sample is intended to be equivalent to trough concentration sampling
197	28-week FU			X	To evaluate elimination of abatacept and immunogenicity signal after stopping the dosing

FU = Safety follow-up; PK = pharmacokinetic

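### The Week 12 MRI window in the RA sub-protocol runs past the first abatacept dose, so Week 12 RAMRIS scores need not be pre-abatacept

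*Combined protocol and SAP*

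**What the plan says.** - **Scan window.** RA 8.1.2.3: "Week 12 and Week 24 MRI exams are to be performed within 7 days of both scheduled Week 12 visit and Week 24 visits". The MRI row of RA Table 2 says "Perform within 7 days of scheduled visit". Neither limits the window to days before the visit.
- **Repeats.** RA 8.1.2.3: "MRI exams with quality issues identified at the investigator site or core imaging lab should be repeated within 7 days of notification". No outer limit is tied to the visit or to abatacept. The same section recommends that sites book two scan appointments a week apart in case one has to be repeated.
- **Start of abatacept.** RA Table 2, footnote k: "First dose of abatacept is to be administered at the Week 12 visit". RA 2.2.1: "All subjects in the RA sub-protocol will also receive open-label abatacept from Week 12 to Week 24". So both randomised arms are exposed.
- **End of blinded treatment.** RA 4.1: "the last day of dosing of branebrutinib or PBO in the RA sub-protocol should be the day prior to the Week 12/Day 85 visit".
- **General order.** RA 8.1: "All assessments should be performed or administered prior to study drug administration unless otherwise indicated". The sequence list under RA Table 2, with dosing last, covers assessments made at one visit.
- **Use of the scan.** RA 9.3.3 lists RAMRIS change from baseline at Week 12, and from Week 12 to Week 24, as additional endpoints. The Week 12 scan serves both.

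**The concern.** The Week 12 scan is the last imaging look at the randomised comparison and the starting point for the abatacept-period change. It should show the subject's state before abatacept. As written, a site that scans a few days after the visit complies with the protocol while imaging a subject already on a second active drug and off blinded treatment. RA 2.2.2 credits abatacept with reducing both signs and symptoms and structural progression in RA, so it cannot be treated as inert for what RAMRIS scores.

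The central readers are blinded to scan order, which is right, but it means that reading will not reveal which scans were late. The text available has no rule to identify or handle them. Imaging may also inform early decisions, since RA 9.4.4 plans a Week 12 lock and an unblinded efficacy review for development planning.

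**Working it through.** **1. The plan's own design figure.** RA 9.1 states 82% power for ACR50, with 15% against 45%, 20 against 60 subjects, one-sided 5%.
- Pooled rate = (20 × 0.15 + 60 × 0.45)/80 = 0.375.
- Null SE = √[0.375 × 0.625 × (1/20 + 1/60)] = 0.125.
- Alternative SE = √[0.15 × 0.85/20 + 0.45 × 0.55/60] = 0.1025.
- Power = Φ[(0.30 − 1.645 × 0.125)/0.1025] = Φ(0.92) = 82.2%.

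The figure reproduces. It does not involve MRI, so nothing below changes it.

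**2. Calendar.** Take the visit on Day 85, the window counted from that visit, and weekly injections. RA Table 10 labels the Day 99 sample "Before the third dose of abatacept", so nominal injections fall on Days 85, 92 and 99. The last blinded dose is on Day 84.

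| Week 12 scan | Day | Days since first abatacept | Injections before scan |
|---|---|---|---|
| At the visit, before dosing | 85 | 0 | 0 |
| After the visit | 86–91 | 1–6 | 1 |
| Last permitted day | 92 | 7 | 1 (2 if after that day's dose) |
| Repeat of a Day 92 scan, notified the same day | up to 99 | 14 | 2 (3 if after that day's dose) |

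The documents give no notification lag. Assuming 3, 7 or 14 days, the repeat of a Day 92 scan could fall as late as Day 102, 106 or 113. That is 17, 21 or 28 days after the first injection, with 3, 3 or 4 injections on earlier days. A Day 92 scan is also 92 − 84 = 8 days after the last blinded dose. The visit's own tolerance of 3 days moves the whole table but not the intervals.

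Of the 84-day abatacept period, 7 days is 7/84 = 8% and 14 days is 14/84 = 17%.

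**3. Share of late scans.** If every site scans on or before the visit and before dosing, the share is 0%. If every site scans afterwards, it is 100%. Spread evenly over 7 days either side, it is 7/14 = 50%, or 7/15 = 47% counting the visit day as its own day. Only the even spread gives about half, and it is an assumption.

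**4. What late scans do to the estimates.** Let π be the share of late scans in an arm and δ the mean shift in score that early abatacept causes in a late scan.
- Between arms at Week 12, the shift in the difference is π_B δ_B − π_P δ_P. If shares and shifts are equal in the two arms, this is zero. If either differs, it can take either sign.
- Within an arm, the Week 12 to Week 24 change moves by −πδ. It shrinks if early and later abatacept effects go the same way.

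The documents give neither π nor δ, so no number can be attached to either line.

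**5. Does other text close the window?** The RA 8.1 rule yields to contrary indications, and a separate 7-day MRI window can be read as one. The sequence list does not reach a scan on another day. Where the protocol wants a one-sided limit it writes one: the baseline ocular tests in pSS 8.1.1.3 may be moved earlier than dosing only, and the Week 12 abatacept PK sample in RA Table 2 is marked predose. The MRI row has no such limit.

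**The case against.** The strongest reply is that RA 8.1.2.3 sits under RA 8.1, so both rules can be met together by scanning in the week before the visit or at the visit before dosing. That reading is available and may be what was meant. It is not the only one, and a site following the MRI row alone would not be told that it applies. The Imaging Manual, a separate SAP and Part 1 of the protocol were not available and may add a timing rule; the protocol should still agree with them.

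The reply is also right about rank. RAMRIS is an additional endpoint. RA 9.4 calls additional endpoints descriptive, although the RA 9.4.1 table also gives them an ANCOVA, and there is no multiplicity-controlled claim on them. Subjects who stop before Week 12 and have an end-of-treatment scan receive no abatacept and are unaffected.

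Two stronger readings are tempting and fail:
- A reader might infer that late scans pull the Week 12 difference towards zero because both arms share an active drug. Sharing alone does not do that. An equal additive shift cancels, as step 4 shows; attenuation would need a floor or other unequal response, which the documents do not establish.
- A reader might infer that at most half the scans are affected, or that late scans generally follow two injections. Step 3 allows up to 100%. With the visit on Day 85, an in-window scan follows two injections only on Day 92 after dosing.

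**Conclusion.** The gap is real and worth closing, but its reach is limited. The protocol permits a Week 12 MRI up to 7 days after abatacept starts, and a repeat 14 or more days after, and the general pre-dose rule does not clearly override this. The Week 12 RAMRIS contrast is therefore not guaranteed to be pre-abatacept, and the Week 12 to Week 24 change may use an on-treatment reference scan.

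This rests on the window being counted from the visit, weekly dosing from that visit, and no overriding rule in the documents not seen. The share of late scans is unknown (0 to 100%), and so are the size and direction of any between-arm bias. The primary endpoint is untouched.

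**What to change.** - In RA 8.1.2.3 and the MRI row of RA Table 2, set the Week 12 window to the 7 days up to and including the Week 12 visit, before the first abatacept injection. Leave abatacept timing as it is. The Week 24 window can stay.
- Place the first of the two recommended appointments early enough for a repeat to precede the injection. With the visit on Day 85, slots on Day 78 (85 − 7) and on Day 85 before dosing fit both the window and the one-week spacing.
- Record each scan date relative to first abatacept and flag any Week 12 scan, including repeats, taken afterwards.
- Report both RAMRIS analyses with and without flagged scans, as a sensitivity analysis. Do not exclude flagged scans by default: under an even spread that could remove about half the Week 12 scans, with only 20 placebo subjects planned. Flagging by date also works for scans already acquired.

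**Cost.** Clarified wording in the protocol and imaging manual, tighter scheduling, and possibly a few more missing or flagged Week 12 scans. Some scans will fall up to a week before blinded treatment ends, which the present window already allows. A failed scan at the visit itself can be repeated only as a flagged scan.
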